## 17.4 Secondary endpoints

### 17.4.1 Confirmatory secondary endpoints

The following two confirmatory endpoints will be tested for superiority of IDegLira vs. IDeg.

- Change from baseline in body weight after 26 weeks of treatment.
- Number of treatment emergent severe or BG confirmed hypoglycaemic episodes during 26 weeks of treatment.

The tests for superiority of the confirmatory secondary endpoints will be based on the FAS and will only be carried out if superiority of IDegLira vs. IDeg with regards to the primary endpoint is confirmed.

In order to control the overall type I error on a 5% level with regards to the secondary endpoints, a hierarchical testing procedure will be used. If superiority is confirmed with respect to change from baseline in body weight after 26 weeks of treatment the number of treatment emergent severe or BG confirmed hypoglycaemic episodes during 26 weeks of treatment will be tested for superiority.

Superiority for change from baseline in body weight will be considered confirmed if the upper bound of the two-sided 95% confidence interval for the estimated mean treatment difference (IDegLira minus IDeg) is strictly below zero or equivalently if the p-value for the one-sided test of

$H_0: D \geq 0.0\%$  against  $H_A: D < 0.0\%$ ,

is less than 2.5%, where D is the treatment difference.

The change from baseline in body weight after 26 weeks of treatment will be analysed using an ANCOVA model with treatment and previous OAD treatment (basal insulin and metformin or basal insulin, metformin and other OAD(s)) as fixed effect and baseline weight as covariate.

Superiority for hypoglycaemic episodes will be considered confirmed if the upper bound of the two-sided 95% confidence interval for the estimated mean treatment ratio (IDegLira vs. IDeg) is strictly below one or equivalently if the p-value for the one-sided test of

$H_0$   $RR \geq 1.0$  against  $H_A$   $RR < 1.0$ ,

is less than 2.5%, where RR is the estimated rate ratio.

The number of treatment emergent severe or BG confirmed hypoglycaemic episodes during 26 weeks of treatment will be analysed using a negative binominal regression model with a log-link function and the logarithm of the time period in which a hypoglycaemic episode is considered treatment emergent as offset. The model will include treatment and previous anti-diabetic treatment as fixed factors and baseline HbA1c as covariate.

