### 1.5 Section 17 Statistical considerations

Rationale: The statistical models for the confirmatory secondary endpoints, hypoglycaemic episodes and dose, have been updated to be in alignment with the models for the global DUAL trials. In addition, clarifications around 1-sided versus 2-sided testing has been added and minor errors corrected.

From section 17:

“Unless otherwise specified, all continuous measurements will be summarised descriptively at each visit by treatment using observed data. After 26 weeks of treatment, descriptive statistics will be presented based both on observed and last observation carried forward (LOCF) imputed data. Endpoints that are analysed untransformed and endpoints that are not formally analysed are

summarised by the arithmetic mean, standard deviation (SD), median, and minimum and maximum value. Endpoints that are analysed log-transformed are *summarised by* ~~supplemented with~~ the geometric mean and coefficient of variation (CV).”

“Presentation of results from a statistical analysis will include the estimated mean treatment effects (Least Square Means [LSMeans]) for absolute values and change from baseline. In addition, estimated mean treatment difference (or ratio) will be presented together with the two-sided 95% confidence interval and corresponding two-sided ~~5%~~ p-value.”

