#### From section 17.4.1 Confirmatory secondary endpoints

The following two confirmatory endpoints will be tested for superiority of IDegLira vs. IDeg.

- Change from baseline in body weight after 26 weeks of treatment.
- Number of treatment emergent severe or BG confirmed hypoglycaemic episodes during 26 weeks of treatment.

The tests for superiority of the confirmatory secondary endpoints will be based on the FAS and will only be carried out if superiority of IDegLira vs. IDeg with regards to the primary endpoint is confirmed.

In order to control the overall type I error on a *two-sided* 5% level with regards to the secondary endpoints, a hierarchical testing procedure will be used. If superiority is confirmed with respect to change from baseline in body weight after 26 weeks of treatment the number of treatment emergent severe or BG confirmed hypoglycaemic episodes during 26 weeks of treatment will be tested for superiority.

Superiority for change from baseline in body weight will be considered confirmed if the upper bound of the two-sided 95% confidence interval for the estimated mean treatment difference (IDegLira minus IDeg) is strictly below zero or equivalently if the p-value for the one-sided test of

$$H_0 D \geq 0.0\% \text{ against } H_A D < 0.0\%,$$

is less than 2.5%, where D is the treatment difference.

The change from baseline in body weight after 26 weeks of treatment will be analysed using an ANCOVA model with treatment and previous OAD treatment (metformin  $\pm$  one other OAD) as fixed factors and baseline weight as covariate.

Superiority for hypoglycaemic episodes will be considered confirmed if the upper bound of the two-sided 95% confidence interval for the estimated mean treatment ratio (IDegLira vs. IDeg) is strictly below one or equivalently if the p-value for the one-sided test of

$$H_0 RR \geq 1.0 \text{ against } H_A RR < 1.0,$$

is less than 2.5%, where RR is the *treatment-estimated* rate ratio.

Number of treatment emergent severe or BG confirmed hypoglycaemic episodes during 26 weeks of treatment will be analysed using a negative binominal regression model with a log-link function and the logarithm of the time period in which a hypoglycaemic episode is considered treatment emergent as offset. The model will include treatment and previous antidiabetic treatment as fixed factors and baseline HbA1c as covariate.

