1.2 Scope of the statistical analysis plan

This Statistical Analysis Plan (SAP) is based on final Protocol version 5.0 (06-Dec-2016).

The scope of this SAP is to add one sensitivity analysis for change from baseline in HbA_{1c} after 26 weeks of treatment and several sensitivity analyses for confirmatory secondary endpoints, and performed other minor changes. For further details on the changes see section [3](#).

2 Statistical considerations

Novo Nordisk will analyse and report data from all sites together.

All analyses of efficacy and safety endpoints will be based on the full analysis set (FAS). The analysis of the primary endpoint and the confirmatory secondary endpoint, change from baseline in body weight after 26 weeks of treatment, will be repeated on the per-protocol (PP) analysis set and the completer analysis set (CAS) for sensitivity purposes. All efficacy endpoints will be summarised using the FAS and safety endpoints will be summarised using the safety analysis set (SAS).

The impact of protocol deviations and outliers may be investigated further in sensitivity analyses if deemed relevant.

Unless otherwise specified, all continuous measurements will be summarised descriptively at each visit by treatment using observed data. After 26 weeks of treatment, descriptive statistics will be presented based both on observed and last observation carried forward (LOCF) imputed data. Endpoints that are analysed untransformed and endpoints that are not formally analysed are summarised by the arithmetic mean, standard deviation (SD), median, and minimum and maximum value. Endpoints that are analysed log-transformed are summarised by the geometric mean and coefficient of variation (CV).

For measurements over time, mean values will be plotted to explore the trajectory over time. LOCF imputed data will be used as the basis for plotting data, if not otherwise specified. For endpoints that are analysed log-transformed, the geometric mean values will be plotted.

A standard analysis of covariance (ANCOVA) model will be applied for the continuous primary and secondary endpoints. The model includes treatment and previous antidiabetic treatment (basal insulin and metformin or basal insulin, metformin and other OAD(s)) as fixed factors and the corresponding baseline value as a covariate. In the following, this model will be referred to as the standard ANCOVA model.

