The number of treatment emergent severe or BG confirmed hypoglycaemic episodes during 26 weeks of treatment will be analysed using a negative binominal regression model with a log-link function and the logarithm of the time period in which a hypoglycaemic episode is considered treatment emergent as offset. The model will include treatment and previous antidiabetic treatment as fixed factors.

As a sensitivity analysis, for withdrawn subjects, the number of episodes in the missing period (time of withdrawal to planned treatment emergent period [max of 27 weeks and longest treatment emergent time observed in the trial]) will be imputed using a multiple imputation technique⁵, and

assuming that all subjects have an event rate in the period before and after withdrawal corresponding to the event rate in the comparator group (IDeg). This will be done as follows:

- As a first step, a Bayes negative binomial model with the same fixed factors used in the original confirmatory analysis model is fitted to the event rate data to obtain the posterior distribution of model parameters.
- In the second step, based on the estimated parameters for comparator (IDeg) in this model, the number of events in the missing period is imputed for all withdrawn subjects. I.e. pre and post withdrawal event rates in the conditional distribution used for imputation are as for comparator (IDeg). Multiple copies (1000 copies) of a complete data set are generated by sampling from the estimated distribution.
- In the third step, for each of the complete data sets, the number of events is analysed using a negative binomial model including the same fixed factors used in the original model.
- In the fourth step, the estimates and standard deviations for the 1000 data sets are pooled to one estimate and associated standard deviation using Rubin's rule⁴. From these pooled estimates the confidence interval for the treatment ratio and the associated p-value are calculated.

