A listing of subjects with at least one post baseline value \geq 20 ng/l will be done. The listing will include age, gender, calcitonin measurements over time and AE history (including preferred term, onset and stop dates).

Urinalysis

Categorical urinalysis parameters will be summarised descriptively by:

- Shift from baseline to EOT (using the number of subjects in the different categories)
- Subjects with at least one post baseline measurement outside reference range will be listed

Insulin and GLP-1 antibodies

Insulin antibodies (IDeg specific, cross-reacting to human insulin and total) will be summarised with arithmetic mean, standard deviation (SD), median, and minimum and maximum value by treatment and treatment week, and their mean over time will be plotted. Correlations will be explored graphically as follows. Insulin antibodies (IDeg specific, cross-reacting to human insulin and total) will be plotted against HbA_{1c} after 26 weeks, HbA_{1c} change from baseline after 26 weeks, and dose after 26 weeks. Change from baseline to FU1 in insulin antibodies (IDeg specific, cross-reacting to human insulin and total) will be plotted against HbA_{1c} after 26 weeks, HbA_{1c} change from baseline after 26 weeks, and dose after 26 weeks.

GLP-1 antibodies (liraglutide specific, cross-reacting to native GLP-1, liraglutide *in vitro* neutralising and *in vitro* neutralising to native GLP-1) will be summarised by number of subjects (N) and percentage of subjects (%) with positive and negative samples.

Antibody measurements will be listed by subject and visit together with associated age, sex, BMI, HbA_{1c} and dose

3 Changes to the statistical analyses planned in the protocol

- Additional sensitivity analysis added to use pattern mixture model to evaluate the sensitivity of using LOCF for primary endpoint HbA_{1c}
- Sensitivity analyses for confirmatory secondary endpoints have been added.
- One minor change regarding the analysis model to the supportive secondary endpoint of 9-point self-measured plasma glucose has been made

4 References

-
- ¹ U.S. Department of Health and Human Services, Food and Drug Administration. Guidance for Industry. Diabetes Mellitus: Developing Drugs and Therapeutic Biologics for Treatment and Prevention, Draft Guidance. 2008.
- ² European Medicines Agency. Committee for Proprietary Medical Products (CPMP): Points to consider on switching between superiority and non-inferiority (CPMP/EWP/482/99). EMEA 2000. 2000.

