 Dependent Variable AVAL
 Covariance Structure Diagonal
 Estimation Method REML
 Residual Variance Method Profile
 Fixed Effects SE Method Model-Based
 Degrees of Freedom Method Residual

Class Level Information

Class	Levels	Values
TRTPN	2	1 2
PREAD	2	BASAL INSULIN + METFORMIN BASAL INSULIN + METFORMIN + ONE OTHER OAD

Dimensions

Covariance Parameters 1
 Columns in X 6
 Columns in Z 0
 Subjects 1
 Max Obs per Subject 453

Number of Observations

Number of Observations Read 453
 Number of Observations Used 453
 Number of Observations Not Used 0

Covariance Parameter Estimates

Cov Parm	Estimate
Residual	0.7569

Fit Statistics

-2 Res Log Likelihood 1171.1
 AIC (Smaller is Better) 1173.1
 AICC (Smaller is Better) 1173.1
 BIC (Smaller is Better) 1177.2

Solution for Fixed Effects

Effect	Pre Trial anti-Diabetic treatment	Planned Treatment for Period	Estimate	Standard Error	DF	t Value
Intercept		01 (N)	4.8895	0.3187	449	15.34
TRTPN		1	-0.9186	0.08674	449	-10.59
TRTPN		2	0			
PREAD	BASAL INSULIN + METFORMIN		-0.2401	0.08191	449	-2.93
PREAD	BASAL INSULIN + METFORMIN + ONE OTHER OAD		0			
BASE			0.3580	0.03449	449	10.38

HbA1c after 26 weeks of treatment - change from baseline - confirmatory statistical analysis - full analysis set - appendix

Parameter Code=C64849B

The Mixed Procedure

Solution for Fixed Effects

Effect	Pre Trial anti-Diabetic treatment	Planned Treatment for Period 01 (N)	Pr > t	Alpha
Intercept			<.0001	0.05
TRTPN		1	<.0001	0.05
TRTPN		2		
PREAD	BASAL INSULIN + METFORMIN		0.0036	0.05
PREAD	BASAL INSULIN + METFORMIN + ONE OTHER OAD			
BASE			<.0001	0.05

Solution for Fixed Effects

Effect	Pre Trial anti-Diabetic treatment	Planned Treatment for Period 01 (N)	Lower	Upper
Intercept			4.2631	5.5159
TRTPN		1	-1.0891	-0.7481
TRTPN		2		
PREAD	BASAL INSULIN + METFORMIN		-0.4010	-0.07910
PREAD	BASAL INSULIN + METFORMIN + ONE OTHER OAD			
BASE			0.2902	0.4258

Type 3 Tests of Fixed Effects

Effect	Num DF	Den DF	F Value	Pr > F
TRTPN	1	449	112.15	<.0001
PREAD	1	449	8.59	0.0036
BASE	1	449	107.71	<.0001

Least Squares Means Estimates

Effect	Label	Margins	Estimate	Standard Error	DF	t Value	Pr > t	Alpha
TRTPN	LSMeans, IDegLira	WORK.ADATA2	7.0585	0.05007	449	140.98	<.0001	0.05
TRTPN	LSMeans, IDeg	WORK.ADATA2	7.9771	0.07082	449	112.65	<.0001	0.05

Least Squares Means Estimates

Effect	Label	Lower	Upper	Exponentiated	Exponentiated Lower	Exponentiated Upper
TRTPN	LSMeans, IDegLira	6.9601	7.1569	1162.68	1053.72	1282.90

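### The confirmatory hypoglycaemia model leaves out baseline HbA1c; adding it before unblinding would be nearly free, but the gain in precision is probably small and may be nil

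*SAP*

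**What the plan says.** SAP section 2.4.1 analyses the number of treatment emergent severe or BG confirmed episodes by negative binomial regression with a log link and log exposure time as offset. Its terms are given as: "The model will include treatment and previous antidiabetic treatment as fixed factors". The multiple-imputation sensitivity analysis in the same section starts from "a Bayes negative binomial model with the same fixed factors used in the original confirmatory analysis model" and analyses each completed data set with those same factors, so it has no HbA1c term either.

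Protocol version 2.0, section 17.4.1, had one term more: "The model will include treatment and previous anti-diabetic treatment as fixed factors and baseline HbA 1c as covariate".

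Elsewhere the SAP does adjust for baseline HbA1c. In section 2.4.2.1 it is a covariate for insulin dose and for every HbA1c responder endpoint, including those that require no severe or BG confirmed episode in the last 12 weeks.

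In the statistical documentation, the confirmatory HbA1c analysis contains baseline HbA1c and reports "Number of Observations Used 453" out of 453 read. The hypoglycaemia fit used 452 of 453.

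**The concern.** The covariate is measured on everyone before treatment and could predict hypoglycaemia. The only support for that in the file is indirect: in the reported dose model, baseline HbA1c predicts insulin dose at week 26 (2.19 units per 1% HbA1c, p<0.0001).

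Randomisation is stratified by previous antidiabetic treatment only (protocol section 11). The cap around 8.5% controls the overall mix of HbA1c, not its split between arms, so balance is left to chance.

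At stake is some precision in the last confirmatory test of the hierarchy, and nothing more. With randomised treatment and no treatment-by-HbA1c interaction, leaving the covariate out does not bias the rate ratio.

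**Working it through.** **1. Reported figure.** The documents give no planned rate, dispersion or power for this endpoint; the sample size section covers HbA1c only. The fitted standard error can be reproduced by inverting the printed Hessian of the confirmatory fit: SE = 0.2948, z = -0.6409/0.2948 = -2.17, two-sided p = 0.0297, rate ratio 0.527 (0.296 to 0.939).

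**2. Spread of baseline HbA1c.** From the HbA1c ANCOVA (residual variance 0.7569, SE of the baseline coefficient 0.03449, 449 df), treating baseline as nearly uncorrelated with the two factors:

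SD = sqrt(0.7569 / (0.03449² × 449)) = 1.19. The mean is 7.0585 + 1.8843 = 8.94.

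**3. Unadjusted SE, for scale.** I read the least-squares mean rates 25.49 and 48.38 as per 100 years. Over 27 weeks (189/365.25 = 0.517 years) they give μ = 0.132 (IDegLira) and 0.250 (IDeg). With n = 300 and 150 and dispersion k = 3.154:

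Var = (1/0.132 + 3.154)/300 + (1/0.250 + 3.154)/150 = 0.0358 + 0.0477 = 0.0834, so SE = 0.2889. This is close to the fitted 0.2948.

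**4. Adjusted SE.** Let b be the assumed slope of log rate per 1% HbA1c and x the centred HbA1c. With total overdispersion held fixed, the residual dispersion is k' = (1 + k)/R - 1, where R = E[exp(2bx)]/E[exp(bx)]². For normal HbA1c, R = exp(b² × 1.19²). The SE comes from the 3 × 3 information matrix for intercept, treatment and HbA1c, with weights m/(1 + k'm) and m = μ·exp(bx)/E[exp(bx)].

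| b (normal HbA1c, either sign) | k' | SE | Fall in SE |
|---|---|---|---|
| 0 | 3.15 | 0.2889 | 0% |
| 0.1 | 3.10 | 0.2883 | 0.2% |
| 0.2 | 2.92 | 0.2867 | 0.7% |
| 0.4 | 2.31 | 0.2805 | 2.9% |

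A 2.9% lower SE is worth 1/0.971² - 1, about 6% more subjects; 0.7% is worth about 1.4%. At b = 0.4 the fall is 2.3% for k = 1 and 4.0% for k = 6. With k = 3.154 it is 1.5% if rates are halved and 5.0% if they are doubled.

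**5. Skewed HbA1c.** Entry requires HbA1c of at least 7.5%, and a mean of 8.94 with SD 1.19 suggests right skew. I assume a gamma distribution shifted to start at 7.5, with the same mean and SD:

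| b | Fall in SE |
|---|---|
| -0.4 | 1.3% |
| -0.2 | 0.5% |
| +0.2 | about 1.3% |
| +0.4 | about 10% |

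The last line depends heavily on the upper tail: 12.1% with no upper limit, but 5.0% if the distribution is cut at an assumed 14%. At +0.2 the same two choices give 1.4% and 1.0%. A slope of 0.4 means a rate change of exp(0.4) - 1 = 49% per 1% HbA1c, which is large.

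**6. Cost if HbA1c is not prognostic.** sqrt(1/(1 - 1/449)) - 1 = 0.1% larger SE.

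**7. The same benefit seen as imbalance.** A one-SE difference between arms is 1.19 × sqrt(1/300 + 1/150) = 0.119 points of HbA1c. It moves the unadjusted rate ratio by a factor of exp(0.119b): 1.01 at b = 0.1 and 1.05 at b = 0.4. This is largely the gain of step 4 in another form, not a second one.

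**8. Type I error.** In 2,000 simulated trials per setting with rate ratio 1 and normal HbA1c, one-sided rejection at b = 0, 0.2 and 0.4 was 3.0%, 3.0% and 3.5% unadjusted, and 3.2%, 3.0% and 3.0% adjusted (Monte Carlo SE about 0.4 points). The two models do not differ.

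**The case against.** The strongest reply is that the simpler model is a legitimate choice. It adjusts for the stratification factor, it matches the supportive hypoglycaemia models (which had no HbA1c term in protocol version 2.0 either), and the amendment to protocol version 3.0 says in its section 1.5 that these models "have been updated to be in alignment with the models for the global DUAL trials". Consistency across a programme is a good reason. It is also true that no gain can be demonstrated from the documents, because every non-zero figure above rests on an assumed slope. Both points stand, and they limit this to an efficiency point.

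A reader might infer something stronger: that the SAP silently departs from the protocol. The amendment text, as printed, still reads "The model will include treatment and previous antidiabetic treatment as fixed factors and baseline HbA 1c as covariate", while SAP section 3 lists among model changes only "One minor change regarding the analysis model to the supportive secondary endpoint of 9-point self-measured plasma glucose has been made". The documents do not support that inference. The amendment announces an update to the hypoglycaemia model, yet as printed its terms are those of version 2.0, so the printed text shows no change. In the same sections, deleted and inserted words are run together: the old and new adjectives before the rate ratio are fused, and so are the old and new plot types for calcitonin. In both places the SAP carries only the new word. The HbA1c phrase may well be struck-out text whose marking was lost. The SAP follows protocol version 5.0, which is not in the file. If the covariate was already removed there, section 3 is right not to list it, and that is the more likely reading.

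**Conclusion.** The point holds as a modest efficiency point. A baseline value that is complete in the full analysis set, and that the SAP uses in related models, is left out of the last confirmatory model. Restoring it before unblinding would be almost free.

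The expected gain is a fall in the SE of the log rate ratio of 0% to 2.9% for slopes of 0 to 0.4 under normal HbA1c. Under right skew it is about 0.5% to 1.3% for slopes of -0.2 to -0.4, and about 1.3% to 10% for +0.2 to +0.4, with the top of that range driven by the assumed tail. These figures take the fitted rates and dispersion for scale and assume no treatment-by-HbA1c interaction. If HbA1c does not predict episodes, the gain is nil and the SE rises by about 0.1%.

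With a reported p of 0.0297, and 0.0419 in the imputation analysis, a reader might infer that the confirmatory result is biased, that its error rate is inflated, or that it would change on adjustment. Nothing in the documents supports any of these. The specified model is valid.

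**What to change.** Before unblinding, extend the sentence in SAP section 2.4.1 so that the model includes treatment and previous antidiabetic treatment as fixed factors and baseline HbA1c as covariate. In steps 1 and 3 of the multiple-imputation sensitivity analysis, refer to the same fixed factors and covariate, so that imputation and analysis match the main model. Extending the covariate to the supportive hypoglycaemia models is optional.

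The cost is three short edits and one degree of freedom. There are no new data, and none of the 452 subjects in the fit is lost. The change would give up the alignment with the global trials. If that alignment is preferred, keep the present model as confirmatory and pre-specify the HbA1c-adjusted model as a sensitivity analysis.

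The file already contains final output dated 22 January 2020. For this trial as it stands, an adjusted fit could only be a labelled post hoc sensitivity analysis, and the completed confirmatory test should be left as it is.
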